3.4.5 Intraoperative Evaluation

Patients that meet the study criteria will receive PhotoFix as a vascular patch, per the IFU. A patient will remain eligible for continuation if PhotoFix remains implanted at the conclusion of their vascular surgery; patients would be considered enrolled at this point. Peri-operative and post-operative (<24 hours after surgery) data will be collected on all enrolled patients; this data will be entered into the Operative Assessment eCRF (Appendix D). The following measures will be monitored and documented per indication, but may include:

- Surgery date
- Implanting surgeon
- Number of PhotoFix Patches Used
- PhotoFix lot number(s)
- PhotoFix patch size(s) (indicated on box(es))
- Patch implant site
- Surgical procedure description
- Concomitant procedure description
- Any adverse events, device malfunctions, or intraoperative mortality
- Peri-operative imaging data

Any intraoperative adverse events will be captured on the Adverse Event eCRF (Appendix D). Patients will be told to contact the investigator in the event of any complications which occur during the study. The contact information for the Principle Investigator is included in the copy of the signed ICF each consented patient will have received.

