Patient demographics and medical history, including medications, comorbidities, pertinent surgical history, and fundamental vascular diagnosis, will be collected at time of consent. Medications will only include drugs of interest and will not require a complete listing. Adverse events will be collected after surgery on all patients consented and enrolled into the study. The investigation will be conducted for a period necessary to collect all follow-up, as needed on each patient, but will not exceed 7 months after surgery. The total time a patient will be followed will be determined by their date of surgery; dates of surgery should occur within 60 days of consent. If the patient's surgery is scheduled after 60 days, a re-screen request must be submitted to the Sponsor. The anticipated final follow-up will be conducted in November 2019, but will ultimately be determined by IRB approvals, site activation, and by rate of patient enrollment.

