6.1 Study Endpoints & Variables

In the case of CEAs, the primary endpoint of the study will be rate of ipsilateral central neurologic events.

- Ipsilateral central neurologic events: Transient ischemic attack, amaurosis fugax, stroke, and symptomatic carotid occlusion.

In the case of all other (non-CEA) vascular procedures, the primary endpoint of the study will be primary patency in the target artery or vein.

- Primary patency (of target vessel): Loss of patency will be determined by the loss of previously palpable pulses, patients presenting with recurrent symptoms, a drop in ABI >0.15 in the case of lower limb artery repair, Doppler ultrasound findings of occlusion, angiography of the affected vessel or a combination of these.

The secondary endpoints of the study will include: overall survival rate, all-cause reoperation rate, device-related reoperation rate, explant rate, restenosis rate, adverse event rate, and secondary patency (HAR only).

- Overall Survival:
 - Early mortality: Death < 30 days following PhotoFix implantation.
 - Late mortality: Death ≥ 30 days following PhotoFix implantation, until last day of follow-up.
- All-Cause Reoperation Rate: The total number of reoperations required in patients over the follow-up period, which include the repair or alteration of the surgical area around the patch.

- **Device-Related Reoperation Rate:** The total number of unplanned reoperations required in patients over the follow-up period, which are determined by the surgeon to be device-related.
- **Explant Rate:** The total number of device explants over the course of follow-up. Explants will include the removal of PhotoFix for any reason after implantation.
- **Restenosis Rate:** The total number of documented cases of stenosis documented as the recurrence of abnormal narrowing of a vessel after corrective surgery.
- **Adverse Event Rate:** The total number of any unfavorable and unintended sign (including an abnormal laboratory finding), symptom, or disease temporarily associated with the use of a device, whether or not related to the device.
- **Secondary Patency (HAR only):** The time from implantation to the point where the access is abandoned.

Statistical analysis will be used to assess all study endpoints as applicable.

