## **2.2. Study Population**

All consented patients will be included in the basic patient demographics summary; this section will include data collected on the Demographics Electronic Case Report Form (eCRF). All patients who receive PhotoFix as part of their vascular repair or reconstruction surgery will be considered enrolled and included in all additional summaries and analyses.

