## 2.9. Definition of Analyses

All analyses will focus on outcomes reported during the follow-up period, after PhotoFix implant. Analyses will summarize data collected through the end of follow-up; analyses at each time point are not planned, unless otherwise indicated.

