### 2.9.2 Secondary Analysis

- **Overall Survival:**

- Percent of patients surviving
  - *Early mortality:* Death  $< 30$  days following PhotoFix implantation
  - *Late mortality:* Death  $\geq 30$  days following PhotoFix implantation

- **All-Cause Reoperation Rate:**

- Percent of patients requiring reoperations
  - Reoperation includes the repair or alteration of the surgical area around the patch.

- **Device-Related Reoperation Rate:**
  - Percent of patients requiring unplanned reoperations that are documented as possibly, probably or definitely, device-related
- **Explant Rate:**
  - Percent of patients requiring device explants
    - Explants will include the removal of PhotoFix for any reason after implantation.
- **Adverse Event Rate:**
  - Percent of patients who experienced at least one adverse event
  - Percent of patients who experienced at least one device-related adverse event
- **Restenosis Rate:**
  - Percent of patients who develop stenosis
    - Stenosis is considered as the recurrence of abnormal narrowing of an artery or vein after corrective surgery.
    - Categorization of stenosis  $\geq 50\%$  will occur if data is available.
- (Hemodialysis Access Repair only)  

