## **2.15. Explant Rate**

Frequency counts and percentages will be presented in a table for enrolled patients. A KM survival curve for freedom from explant will be estimated for all enrolled patients. Additional KM plots for freedom from explant may be estimated by surgical indication but will be determined by the sample size of each subgroup; however, it is unlikely that the sample size will be large enough for subgroup analysis.

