## **2.17. Adverse Events**

Adverse events will not be coded. The incidence of adverse events will be summarized for the aggregate sample. Adverse events will be considered as any event happening during or after PhotoFix implant. Any adverse event that occurs prior to surgery will not be included in the summary or analysis.

Adverse events will be summarized based on timing, in relation to surgery. Events will be categorized as early if the event occurs  $< 30$  days after surgery, while late post-operative events will be considered as events occurring  $\geq 30$  days after surgery.

Adverse events will be summarized by pre-specified category; events classified as other will be manually classified, as deemed appropriate. The following will be included in the summary of adverse events: consequence of event, required drug treatment or intervention, severity, relation to surgery, relation to PhotoFix, and status of event at end of study. Events deemed to be related to PhotoFix, with any definitive assessment, will be summarized in a frequency table; additional information discovered during event investigation will be described, as deemed necessary.

Adverse event rate will be presented as frequency counts and percentages in a table for enrolled patients. Adverse events will be presented in aggregate and by surgical indication.

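### Protocol 3.4.5 enrols a patient only if the patch is still in place at the end of surgery, while SAP 2.2 enrols every recipient; applying the protocol rule would drop index-surgery removals from the explant rate

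*Protocol*

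**What the plan says.** The two documents define enrolment differently. Protocol 3.4.5 (Intraoperative Evaluation) sets this rule: "patient will remain eligible for continuation if PhotoFix remains implanted at the conclusion of their vascular surgery; patients would be considered enrolled at this point". The following sentence collects operative and early post-operative data, on the Operative Assessment eCRF, for enrolled patients. Protocol 3.2 takes the same population for adverse events: "Adverse events will be collected after surgery on all patients consented and enrolled into the study". Protocol 4.3 also writes its reporting rules for enrolled patients.

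SAP 2.2 sets no condition on the patch at closure: "All patients who receive PhotoFix as part of their vascular repair or reconstruction surgery will be considered enrolled". These patients then enter every summary beyond basic demographics. SAP 2.15 tabulates explants for enrolled patients and adds: "A KM survival curve for freedom from explant will be estimated for all enrolled patients".

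For the endpoint itself, Protocol 6.1 reads: "The total number of device explants over the course of follow-up. Explants will include the removal of PhotoFix for any reason after implantation". Protocol 4.2 and Appendix E define explant as removal whatever the reason, with no time limit. SAP 2.9.2 expresses the rate as "Percent of patients requiring device explants".

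The forms foresee the case. Item 5 of the Operative Assessment eCRF (Protocol Appendix D) records the patch as implanted or explanted at the end of the operation, and the second answer leads to the Explant eCRF. No section says which definition of enrolment takes precedence.

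**The concern.** The protocol rule makes membership of the study population depend on a device outcome. A patient whose patch is implanted and then removed before the operation ends has had a device removal, yet under 3.4.5 is never enrolled. The protocol also does not fit its own form: if operative data are collected only on patients who leave surgery with the patch, no patient in that group could ever have the explanted answer to item 5.

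This matters because the study is a post-market safety evaluation. Protocol 4.1 lists leakage at the suture line and tissue failure or rupture among the complications specific to PhotoFix, and the Explant eCRF offers suture line tear and rupture as reasons for removal. Such events can occur during the index operation. The explant rate is the summary most exposed, since with few events one case changes the figure visibly.

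**Working it through.** **The plan's own figure.** Protocol 3.2 aims for 100 patients, with 33% screen failure and 10% early termination. 100 / ((1 − 0.33) × (1 − 0.10)) = 165.84, which rounds up to the stated 166. The point made here does not change that number. It also implies about 166 × 0.67 = 111.2 patients past screening, used below as a second denominator.

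**Notation (all counts assumed).** N = patients who receive PhotoFix; k = patients whose patch is removed during the index surgery; e = other patients with a later explant. The documents give no value for k or e.

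- Protocol 3.4.5 rule: e / (N − k).
- SAP 2.2 rule, with index-surgery removals counted as explants: (e + k) / N.

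**Direction.** (e + k)/N − e/(N − k) = k(N − e − k) / [N(N − k)]. Since e + k cannot exceed N, this is never negative. The protocol rule can therefore only lower the rate.

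**Size, N = 100.**

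| k | Protocol rule, e = 0 | SAP rule, e = 0 | Protocol rule, e = 1 | SAP rule, e = 1 |
|---|---|---|---|---|
| 0 | 0/100 = 0% | 0/100 = 0% | 1/100 = 1.00% | 1/100 = 1.00% |
| 1 | 0/99 = 0% | 1/100 = 1.00% | 1/99 = 1.01% | 2/100 = 2.00% |
| 2 | 0/98 = 0% | 2/100 = 2.00% | 1/98 = 1.02% | 3/100 = 3.00% |
| 3 | 0/97 = 0% | 3/100 = 3.00% | 1/97 = 1.03% | 4/100 = 4.00% |

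With e = 1 the differences are 0, 0.99, 1.98 and 2.97 percentage points. With N = 111, e = 1 and k = 1 the rates are 1/110 = 0.91% and 2/111 = 1.80%, a difference of 0.89 points.

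**Precision.** The exact 95% interval is 0 to 3.66% for 0/99 and 0.03 to 5.45% for 1/100. The intervals overlap widely. The practical difference is between reporting no removal and reporting one.

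**Chance that the case arises.** If the true index-surgery removal rate were 1%, 2% or 3% (assumed), the chance of at least one among 100 recipients, 1 − (1 − p)^100, would be 63%, 87% or 95%.

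**Adverse event rate.** Suppose 20 retained patients have an event and the one removed patient also has one (assumed). The rate is then 20/99 = 20.2% under the protocol rule and 21/100 = 21.0% under the SAP rule, which is a small change.

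**The case against.** The strongest reply is that the SAP defines enrolled for its own purposes, and a document's own population definition normally governs its own tables. On that reading SAP 2.15 and 2.17 already include these patients, and 3.4.5 only describes who goes on to follow-up. This largely stands, so a reader who inferred that neither definition governs the explant table would go too far. What remains is that 3.4.5 does more than set continuation. It fixes the point of enrolment, and data collection and adverse event reporting at the sites are then tied to that word. Sites work from the protocol.

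A reader might also infer that such a removal would disappear from the record or the report. The documents do not support that. Item 5 of the Operative Assessment eCRF, the statement in 3.4.5 on intraoperative adverse events, and Table 2 footnote 3 all provide for recording it. Protocol 4.1 undertakes to summarize all complications, with no restriction to enrolled patients, and treats explant as a consequence of one. SAP 2.17 adds: "Adverse events will be considered as any event happening during or after PhotoFix implant".

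Nor is it open whether a removal at the index surgery is an explant. Protocol 6.1 refers to the course of follow-up and SAP 2.9 says "All analyses will focus on outcomes reported during the follow-up period, after PhotoFix implant", but 4.2 and Appendix E cover any removal, and the SAP's period runs from implant, not from closure. An event at time zero is simply a drop at the origin of the Kaplan-Meier curve.

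Finally, it could be argued that these patients might be classed as screen failures and so receive the reduced source verification of Protocol section 7. That is conjecture: screening is pre-operative, and the End of Study eCRF allows discontinuation at Visit 2.

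**Conclusion.** The inconsistency is real and stands in the current text of both documents. Its consequence is limited. If the protocol rule is applied, an index-surgery removal leaves both numerator and denominator of the explant rate, and the bias can only be downward. The size is about 1 percentage point per case with 100 recipients and zero if no patch is removed during surgery. The number of such cases is an assumption throughout.

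The documents do not support saying that these events will be lost, only that a site or analyst following 3.4.5 would leave them out of this rate. The planned summaries are descriptive, so no test is affected. It is still worth correcting, because a safety study should not select its population on a device outcome, and the rule should be settled before results are known.

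**What to change.** Change Protocol 3.4.5 to match SAP 2.2: every patient who receives PhotoFix is enrolled for operative, adverse event and explant data. Keep the patch being in place at the end of surgery only as the condition for continuing to the follow-up visits. Protocol 3.2 and 4.3 already refer to enrolled patients, so they follow the new definition without further change.

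Add one sentence to SAP 2.15: a removal during the index surgery counts as an explant, with all recipients as the denominator, and is shown on its own line. The separate line lets a reader tell removals in the operating room from those during the six months of follow-up.

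The cost is two short wording changes and one table line, since the eCRF fields already exist. The downside is a slightly less favourable explant figure if such a case occurs, and a little extra data entry.

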3.4.6 Follow-up Visits

The patients will be asked to return for 3 post-operative visits at 1, 3, and 6 months after surgery. Available data from post-operative imaging reports will be collected, as is applicable to the study and entered into the Imaging Evaluation eCRF (Appendix D); the imaging is not a requirement of the study. Clinical data for all follow-up visits will be entered into the Follow-Up Evaluation eCRF (Appendix D). This form will collect data on post-operative recovery. The following measures will be monitored and documented per indication, but may include:

- Visit date
- Study status
- Loss of patency/ Evidence of restenosis
- Reoperations / vascular surgeries required post-op
- Any adverse events, explants, or other mortality
- Post-operative imaging data

4 ANTICIPATED COMPLICATIONS AND ADVERSE EVENTS

4.1 Anticipated Complications

For this study, a complication is defined as the following: morbid event or consequences of a morbid event. While all complications will be summarized in the final report, the primary focus of the analysis will be complications involving the vascular system, such as transient ischemic attack (TIA), amaurosis fugax, stroke, symptomatic carotid occlusion, thrombosis, bleeding, and death. The terms “adverse event” and “complication” will be used interchangeably.

An Adverse Event (AE), Unanticipated Adverse Effect (UAE) and Serious Adverse Event (SAE) are defined in Appendix E. All AEs, UAEs and SAEs that occur during the course of the study (until the completion of the final follow-up visit), whether observed by the investigator or by the patient, and whether or not thought to be PhotoFix related, will be reported in detail on the Adverse Event eCRF and followed to a satisfactory resolution. The investigator will follow the patient until the event resolves. In the unusual circumstance that the event has not resolved by the time of the patient’s completion of the study, an explanation will be entered on the Adverse Event eCRF; the circumstance may be determined to be a permanent condition, and will be documented as such.

Secondary morbid events will not be included in the calculation of device-related complication rates. A morbid event should be documented only once unless there are multiple occurrences of that event.

Consequences of morbid events, such as explant, mortality, and reoperation will be captured on the Adverse Event eCRF, which details the associated event. In the case of an explant, additional information will be captured on the Explant eCRF (Appendix D).

Potential complications that may occur with any vascular surgery include, but are not limited to:

- Allergic reaction to medication
- Bleeding
- Breathing difficulty
- Chest pain
- Heart attack
- Infection (ex. pneumonia, urinary tract infection, wound infection)
- Irregular heartbeat
- Lung or kidney failure
- Memory loss
- Pain
- Sickness/ nausea
- Stroke
- Thrombosis

Complications specific to the use of the PhotoFix may include, but are not limited to the following:

- Abscess
- Adhesion

- Blood leakage through suture line, holes, or tears
- Calcification/mineralization
- Complete heart block (arrhythmia)
- Death
- Inflammatory immune response
- Infection
- Intimal hyperplasia
- Rejection
- Tissue damage/degradation
- Tissue failure or rupture
- Toxic response/reaction
- TSE transmission/ variant Creutzfeldt-Jakob disease

The likelihood of any complication is specific to the indication of surgery.

4.2 Consequences of Morbid Events:

Morbid events can result in mortality or the permanent cessation of all vital bodily functions. Morbid events can also require reoperation. Reoperation includes any operation that repairs, alters, or replaces a PhotoFix patch. Morbid events can also require explant. Explant includes any removal of the patch for any reason. Details on the consequences of any morbid event will be captured in the Adverse Event eCRF and Explant eCRF, as applicable (Appendix D).

4.3 Reporting Expectations

Adverse events will be reported per the following guidelines for all enrolled patients:

1. Any (potential) AE must be reported to CryoLife as soon as possible, but no later than 10 working days after knowledge of occurrence, by entry into the EDC.
2. Any UAE, SAEs or AEs of special interest (i.e. vascular complications) must be reported to CryoLife within 24 hours after gaining knowledge of the event, by email or telephone, in addition to entry into the EDC.
3. De-identified source documentation (i.e., physicians/nurse notes or summaries) regarding an AE, UAE or SAE should be provided in addition to the eCRF. The source documents can be uploaded into the eCRF (as a single file) or sent by e-mail to CryoLife.
4. Any patient death will also be reported on the Adverse Event eCRF (requested death certificate and autopsy report, if performed, should also be provided).
5. Additionally, all events shall be reported to the reviewing IRB per their reporting requirements (definitions and timelines).

Report all (potential) AE, UAE or SAE to:

[name]
Clinical Research Project Manager
CryoLife
[contact]
E-mail: [contact]

5 RISK/BENEFIT ANALYSIS

5.1 Benefits

A decellularized, photo-oxidized bovine pericardium potentially offers benefits similar to autologous pericardium (i.e., similar texture, nonimmunogenic, and biocompatible) without the disadvantages of glutaraldehyde treated tissue; the additional (not naturally-occurring) aldehyde residue from glutaraldehyde can interact with surrounding tissue, which leads to membrane damage and trapping of calcium (Ca^{2+}) on residues.¹¹ Design features of PhotoFix may increase the durability and functionality of the device:

- Photo-oxidation: Processing creates crosslinks and stabilizes the internal collagen structure, while eliminating toxic by-products that create sites where calcium can bind to the tissue.

The calcification potential of glutaraldehyde-fixed bovine pericardium is well known.^{12,13} Preclinical results have shown that PhotoFix implanted in a cardiac sheep model demonstrated no evidence of collagen degradation, thrombogenicity, infection, excessive inflammation or intrinsic calcification in the 20-week follow-up period. PhotoFix may have enormous potential for clinical use. The long-term benefits of the unique features of PhotoFix are currently hypothetical.

5.2 Risks

Risks and complications related to vascular surgery are extensively documented in the medical literature. Complications specific to the use of PhotoFix may include, but are not limited to, the following: abscess, adhesion, blood leakage through suture line/holes/tears, calcification /mineralization, complete heart block (arrhythmia), death, inflammatory immune response, infection, intimal hyperplasia, rejection, tissue damage /degradation, tissue failure /rupture, toxic response/reaction, and TSE transmission/ variant Creutzfeldt-Jakob disease. The likelihood of each event is dependent on the specific surgical indication.

5.3 Minimization of Foreseeable Risks

Each physician must consider all the risks and benefits to the patient on an individual basis, when choosing a vascular patch. Efforts will be made to minimize these risks by selecting Investigators who are experienced in vascular surgery. In addition, efforts will be made to ensure that the treatment and follow-up of all patients will be consistent with current medical practice.

All procedures will be performed on patients who are candidates for vascular surgery, requiring the use of a patch. Patients will be carefully monitored throughout the follow-up period and any complications related to the study will be documented and evaluated.

